Name of project	Validation of AVAS classification by using machine learning in prediction of vascular access creation and in the prediction of uninterrupted use of the vascular access for dialysis
Acronym of the project	VAVASC trial (Validation of the Arterio Venous Access Stage Classification) trial
Web page	www.vavasc.com
ClinicalTrial identifier	NCT04796558
Leader of the project	[name], [name], [name],
Type of the study	Prospective, multi-centre, international, collaborative
Registration	None
Number of patients included	Minimum 500, optimal 1000
Start of the study	2021
Estimated end of the study	2023-2024
Ethics committee approval	
Yes. This should be reviewed in each centre, and if necessary each centre should have approval of its own ethics committee.
 
However, please note that this is an observational study that is collecting data from existing medical records. In many centres (e.g. those with routine ultrasound arteriovenous mapping) there will be no alteration to patient care. There is therefore unlikely to be a requirement for patient information or consent.
 
If ethical approval is required in individual centres it could potentially be obtained from a Proportionate Review Service. If applicable, participating units should also register with local audit/clinical governance structures and gain permission from the Caldicott Guardian.

Informed consent	Depends on the centre and decision of the ethical board of each centre
Database (data storage)	Electronic database - eCRF ([name])
Statistic analysis	Predictive modelling by using machine learning ([name], [name])
Financial support	No

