
Background
	
Ultrasound of upper limb vessels as a part of preoperative assessment of patients referred for arteriovenous access placement has been recommended repeatedly in several studies and guidelines. Each patient needing arterio-venous access (AVA) is unique and has different possibilities for fistula creation that depend on many factors as well the anatomical condition of inflow arteries and outflow veins, the so-called ‘arteriovenous access map’. In 2020 we created, published and retrospectively evaluated the inter-rater reliability of the AVAS classification, which is a simplified way of sharing the information about suitability for access creation depending on vascular anatomy (doi: 10.1093/ckj/sfaa189).
 
However, before routine use of the AVAS classification system in clinical practise it requires prospective validation and comparison with other clinical factors. Finally, whether the AVAS classification can be used for the prediction of vascular access function as defined by uninterrupted use of vascular access for dialysis without need for any access intervention/procedures (SONG-HD, doi: 10.1053/j.ajkd.2017.12.003) remains to be tested.
 
This project has two main parts:
 
 1. Validation of AVAS classification with and without combination with other factors using a predictive statistical model. 2. Validation of AVAS classification in terms of prediction of uninterrupted use of successfully created vascular access for dialysis. 
The data will be collected prospectively. Both parts of the project will be taking place simultaneously.

Working hypothesis
	
Part 1: AVAS classification with/without selective clinical parameters is a useful tool for sharing information about the type of AVA which will be created.
 
Part 2: Increasing AVAS with/without selective clinical parameters is an accurate predictive tool for the prediction of the uninterrupted use of successfully created vascular access for dialysis.

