	
 - Height: - Weight: - BMI: - Diabetes: Yes No - CV line previous or current Yes No - Side of the CV line if place Left Right 
Non-obligatory parameters (parameters B):
 
 - Smoking history: Yes No - Hypertension: Yes No - Heart failure: Yes No - Ischemic heart disease: Yes No - Cancer (previous or current): Yes No 
In order to evaluate uninterrupted use of the vascular access for dialysis (part 2 of the study), we will follow the patients and do a time to event analysis of the arteriovenous accesses for one year after creation or up until the first intervention for maintaining patency has been performed. If the patient dies during follow up the date of death should be recorded. The data for this part will be collected prospectively (Belfast City Hospital, UK, University hospital Královské Vinohrady Prague, CZ and other centres).
 
Predictive models will be used for validation of AVAS classification. The data will be registered via eCRF and analysed by [name] and [name]

Methodology step-by-step
	
 1. Patient with need of AVA creation is assessed in outpatient clinic as usual. 2. To reduce bias all consecutive patients must be captured. 3. Each registered health care professional (HCP) in the participating centre in the VAVASC study has access to eCRF (electronic database). They can fill the collected data straight into the database or at a later date from the notes they usually take when recording arteriovenous mapping. If the HCP or centre prefers paper forms, a paper document (VAVASC FORM) can

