	
be used and researchers from each centre will put the data from the paper form into the eCRF regularly. Collection of data into eCRF primarily is the preferable approach. If the HCP examining the patient has access to eCRF, they do not have to fill the paper VAVASC FORM.
 
4. Patient is scanned using ultrasound and the vascular parameters are marked/registered (eCRF or VAVASC FORM). If the HCP wishes, they can evaluate the patient according to AVAS classification. The HCP can skip this step since the vascular parameters can be used to establish the AVAS by the VAVASC research group.5. Patients' risk factors are also marked/registered. Only “obligatory parameters” (parameters A) are necessary to collect. The HCP can also collect the parameters B, that are voluntary. 
For centres using paper form (VAVASC FORM)
 
- If the centre/individual HCP prefers paper forms only, VAVASC FORM is stored in a prepared box in each clinic in the hospital entitled as “VAVASC”.- Researcher from each centre regularly collects the VAVASC FORM documents.- Researcher from each centre regularly enters obtained data from VAVASC FORM into the eCRF.- A similar approach may be used by centres that already record the information on the VASVASC form elsewhere (e.g. the medical records or centre specific arteriovenous maps) 
6. Patient is indicated for AVA as usual (not necessarily as is indicated by AVAS)7. Researcher from each centre regularly follows up the patients and enters type of AVA which was created into the eCRF.8. Researcher from each centre regularly follows up the patients and enter data about the fate of AVA for one year or up until the first intervention for maintaining
--	---

	patency has been performed. If the patient dies during follow up the date of death should be recorded.
Statistic method	Predictive modelling using machine learning ([name], [name])

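### AVAS may be scored before the access is chosen, and no shown text withholds the score or records whether it was known, so Part 1 agreement could be inflated by an unknown and possibly zero amount

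*Protocol*

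**What the plan says.** The Part 1 hypothesis in the protocol (Working hypothesis) is that AVAS, with or without clinical parameters, "is a useful tool for sharing information about the type of AVA which will be created". The matching outcome is collected in step 7 of the step-by-step methodology, where the centre's researcher "enters type of AVA which was created into the eCRF".

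AVAS can be scored in two ways under step 4, which covers the ultrasound scan. Locally: "If the HCP wishes, they can evaluate the patient according to AVAS classification". Centrally: "The HCP can skip this step since the vascular parameters can be used to establish the AVAS by the VAVASC research group". The choice of access follows in step 6: "Patient is indicated for AVA as usual (not necessarily as is indicated by AVAS").

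Three other places bear on the point. The ethics entry expects that in many centres "there will be no alteration to patient care". Step 3 lets data be entered "at a later date from the notes they usually take when recording arteriovenous mapping". The Background describes AVAS as "a simplified way of sharing the information about suitability for access creation depending on vascular anatomy".

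The lists of obligatory and voluntary parameters, and steps 4 to 8, contain no item on whether AVAS was scored or known before the access was chosen. The one bias control that the text names is consecutive capture of patients.

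**The concern.** When the outcome of a validation study is a clinician's decision, knowing the predictor can change the outcome. Here the tool under test may be available to the person whose decision it is meant to predict. If the score moved a choice that the vessel map alone would not have moved, that patient counts as a success for AVAS partly because AVAS was used.

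Most agreement between AVAS and the access created would not be of this kind. AVAS and the usual choice both draw on the same vessel anatomy, and agreement for that reason is legitimate prediction.

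At stake is how Part 1 can be read. Recruiting more patients narrows the interval but leaves this bias in place. A later analysis plan can choose models and subgroups, but it cannot reliably reconstruct who knew the score if that was not noted at the time. That makes it a data-capture matter for the protocol and forms.

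**Working it through.** **Reading the steps together**

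1. Exposure possible? Step 4 permits a local score at the scan and is listed before step 6. So the order as written allows it, though it does not require it.
2. Exposure blocked? Step 6 keeps usual practice and says AVAS need not be followed. That makes the score non-binding; it does not blind the chooser. Consecutive capture deals with selection, not with knowledge of the score.
3. Exposure recorded? Not in the shown parameter lists or steps. The form and eCRF fields are not shown and might hold it.
4. Outcome open to influence? Yes: the type of access is chosen by a person.

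**Illustration of size**

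The protocol gives no figure to reproduce; it states only a minimum of 500 and an optimum of 1000 patients. Every other input is my assumption. Raw agreement is a simple stand-in, since the protocol names only machine-learning prediction.

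- a = agreement when AVAS is unknown to the chooser (assumed 60–80%)
- k = share of decisions with AVAS known (assumed 0–100%)
- c = share of otherwise discordant choices that knowing AVAS converts (assumed 0–50%)

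Inflation = k × c × (1 − a).

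| Case | a | k | c | Inflation (points) |
|---|---|---|---|---|
| Score never known | any | 0 | any | 0 |
| Score adds nothing to the map | any | any | 0 | 0 |
| Low | 70% | 50% | 10% | 0.50 × 0.10 × 0.30 = 1.5 |
| Middle | 70% | 50% | 25% | 0.50 × 0.25 × 0.30 = 3.75 |
| Top if c is at most 30% | 60% | 100% | 30% | 1.00 × 0.30 × 0.40 = 12 |
| Top if c is at most 50% | 60% | 100% | 50% | 1.00 × 0.50 × 0.40 = 20 |

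The top value simply follows the ceiling chosen for c, and k = 100% is unlikely when scoring is optional.

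For scale, the 95% half-width at 70% agreement is 1.96 × √(0.70 × 0.30 / n):

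- n = 500: 4.02 points
- n = 1000: 2.84 points

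With a = 70% and c = 25%, inflation is 7.5 × k points. It equals the half-width at k = 4.02/7.5 = 0.54 for 500 patients and at k = 2.84/7.5 = 0.38 for 1000. The middle case is therefore slightly below sampling error at the minimum size and above it at the optimum.

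**The case against.** The strongest reply is that the causal route is inferred. Bias needs a score that exists before the decision, reaches the chooser, and changes the choice. The protocol states none of these. The order comes from a numbered list that is not strictly chronological, since steps 2 and 3 are standing rules. Later data entry means that some scores may follow the decision. The responsibilities section gives the clinic HCP the mapping and recording, not the choice, and the paper route described runs from form to researcher to eCRF. Step 6 also shows that the authors considered AVAS-driven choice and directed usual care.

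All of this stands, and it is why the amount may be zero. It does not close the gap. None of these passages withholds the score, and the protocol presents AVAS, and classification generally, as a means of sharing information between those caring for the patient, so a route to the chooser is plausible.

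A reader might infer more than the text supports:

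- *That AVAS drives the choice, so Part 1 is circular.* Nothing in the document shows that the score reaches the chooser or changes anything.
- *That affected patients can never be identified.* This depends on forms not shown. A separate field for a local score would give at least a proxy.
- *That the upper figures measure the bias.* They only reflect assumed inputs.
- *That deriving AVAS centrally would cure it.* Central derivation makes the predictor consistent, but the decision may already have been exposed.

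**Conclusion.** The concern holds in a limited form. As written, the plan allows the tool under test to influence the outcome it is tested against, and the shown text neither prevents this nor records where it could have happened. The direction, where it occurs, is towards agreement that is too high.

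The size is unknown and possibly zero. The illustrative middle case of 3.75 points shows only that an effect comparable with sampling error is conceivable; it is not an estimate. The conclusion rests on the step order as listed, on no masking rule existing outside the shown text, and on the forms not already holding the item. It is a worthwhile, inexpensive improvement and does not invalidate the study.

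**What to change.** 1. **Step 4.** Where AVAS is not already routine in a centre, ask that any optional HCP score be made only after the access decision has been noted. The analysis loses nothing, because the research group can establish AVAS from the vascular parameters, and usual care is unchanged.
2. **eCRF and VAVASC FORM, unless already present.** Add one item, noted at indication: *AVAS known to the person choosing the access before indication (yes / no / unknown)*. It may be transcribed later, as step 3 allows, provided that the answer was noted at the time.
3. **Reporting.** Keep all consecutive patients. Report Part 1 performance overall and, as a sensitivity analysis, in patients whose AVAS was not known.

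Deriving AVAS centrally, without sight of the access created, is sensible for consistency but is not a remedy for this bias.

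**Cost.** One added item, a note of the decision at indication (step 7 now asks only for the access created), and a few lines of wording. Centres working from existing records may often answer *unknown*.

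The subgroup results will be imprecise. If 25% of 500 knew AVAS, the 95% half-width at 70% agreement is 8.0 points for those 125 and 4.6 for the other 375. To detect the assumed difference of 77.5% (0.70 + 0.25 × 0.30) against 70%, a two-sided 5% test of two proportions has this power:

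| Split known / not known | N = 500 | N = 1000 |
|---|---|---|
| Even | 48% | 77% |
| 25% / 75% | 36% | 63% |

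A non-significant difference would therefore not show absence of influence. The comparison is also not randomised and is confounded by HCP and centre.

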Responsibilities of the research team	
 1. The centre lead registers interest with VAVASC research group, and will seek local ethical approval. 2. Centre lead is responsible for ensuring the required data is collected by HCPs in the clinic, and supervising the data collectors in their centre. 3. HCP in the clinic: Carries out arteriovenous mapping and records clinical data. 4. HCP in the clinic or data collector fills the paper VAVASC FORM/ or fills the data into eCRF (computer) database, approx. 10 minutes. 5. Data collector in each centre where eCRF is not used: may collect the VAVASC FORM and enter data into the eCRF, approx..1 hour/week 6. Centre lead or data collector in each center regularly checks the patient follow up, approx. 1 hour/week 7. Project leader of VAVASC group: regularly sends informative email about status of the study to all researchers (how many patients recruited, how many centres are active etc.). 8. VASVASC group will analyse results and prepare manuscript.
Authorship	
Named author is a HCP who acts as a centre lead, and sets up the study in their centre including ethical approval. This HCP is also invited into the writing group, so they are able to participate in drafting and reviewing the final manuscript.
 
Collaborator /collaborative author (also PubMed citable) is a HCP who collects patient data and enters the data in the eCRF or provides the data to the centre lead for entry. To reduce bias collaborators must capture consecutive patients. There is no minimum or maximum amount of consecutive patients that could be entered by a collaborator. However, each collaborator must collect data for patients who have

	
gone onto have successful vascular access creation and these patients must be followed up for the full follow up period. Unfortunately, in some cases attempts at vascular creation will fail so collaborators are encouraged to recruit as many consecutive patients as they can. To avoid disadvantaging and excluding low volume centres (which would impact the generalizability of the study) no time limit will be set for recruitment of consecutive patients. However, the eCRF will close to further data entry on X.

--	---

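### Step 4 lets AVAS, the predictor under validation, come from two sources, and does not require the research group's staging to be done without sight of the outcomes

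*Protocol*

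**What the plan says.** All references are to the protocol.

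- **Who stages (Methodology step-by-step, step 4).** The clinic scans the arm and "the vascular parameters are marked/registered (eCRF or VAVASC FORM"). Staging in the clinic is voluntary: "If the HCP wishes, they can evaluate the patient according to AVAS classification". If it is left out, the group can do it: "The HCP can skip this step since the vascular parameters can be used to establish the AVAS by the VAVASC research group".
- **When data arrive (step 3).** Mapping data may be typed in directly or later from the clinician's notes. No deadline is set relative to creation of the access.
- **Where the outcomes go (steps 7 and 8).** A centre researcher "enters type of AVA which was created into the eCRF", and a centre researcher is also to "enter data about the fate of AVA for one year", or until the first intervention to maintain patency.
- **One data system (Methodology).** "The data will be registered via eCRF and analysed by" two named analysts.
- **Who reports (Responsibilities of the research team, item 8).** "VASVASC group will analyse results and prepare manuscript".
- **Earlier work (Background).** The project's authors state that they created AVAS, published it and "retrospectively evaluated the inter-rater reliability of the AVAS classification". No result is given.

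**The concern.** AVAS is both the object of validation and the main predictor in the two parts. A validation is only as clear as the definition of who assigned the predictor and what they knew at the time.

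Step 4 leaves two routes open. First, the analysed stage may be the clinician's for some patients and the research group's for others. A result from such a mixture describes neither staging by clinicians in practice nor staging by one central rule. Second, the group may stage a map when the access type, or even the follow-up, is already recorded. If a map could reasonably fall in either of two stages, knowledge of the access made could tip the choice. Outcome information would then leak into the predictor. That raises apparent accuracy in Part 1 directly, and could do so in Part 2 through knowledge of how the access fared.

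The issue is grading of the predictor after the outcome. It is not whether a clinician's AVAS score influences the choice of access.

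**Working it through.** The protocol gives no figure on this point, so there is none to reproduce. The check is to set the provisions side by side.

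1. **Source.** Step 4 allows the clinician to stage and allows the group to stage. No sentence says which value is analysed when both exist, and none says that the group stages everyone. Both a single-source and a two-source predictor comply with the text.
2. **Sequence.** Central staging needs the vessel parameters. Step 3 allows these to be entered late, with no limit tied to surgery. Steps 7 and 8 add the outcomes as they occur. Staging before the outcome and staging after it both comply.
3. **Information.** The vessel parameters and the access type are in the same eCRF, and follow-up data are registered there too. No sentence requires the stager to work from a view without the outcome fields. No sentence describes access rights, so it is not stated that stagers see those fields either.
4. **Roles.** The group that may stage is also the group that analyses and writes up (step 4 and Responsibilities, item 8). The overlap is shown for the group only. Whether the two named analysts also stage is not stated.

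**Illustration of size, Part 1 agreement only.** Let
- s = share of borderline maps staged by the group with the outcome known,
- b = share of maps that are borderline between two stages,
- a = agreement with the access made, in borderline maps, if staged blind.

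If every such map is resolved toward the access made, the gain in overall agreement is s × b × (1 − a).

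None of the three inputs is in the document; all are assumed. With a = 0.50 and s = 1:
- b = 0.10: 1 × 0.10 × (1 − 0.50) = 0.05, or 5 points;
- b = 0.20: 1 × 0.20 × (1 − 0.50) = 0.10, or 10 points.

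These are upper bounds for the assumed a and b, because they take s = 1 and resolution always toward the outcome. They shrink in proportion to s. With fully mechanical staging b = 0, so the gain is zero. No comparable figure can be given for the time-to-event outcome in Part 2.

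**The case against.** The strongest reply is that the protocol can be read as single-source. The Methodology says that vessel parameters are collected so that AVAS can be evaluated, which makes them the study data and the clinician's score an optional extra. Central derivation for every patient fits this and fits step 4. That stands: a reader might infer that the predictor is in fact mixed, but the verb in step 4 is permissive and does not establish it.

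A reader might also infer from the Background that the project regards AVAS as rater-dependent. It does not say so. Evaluating reliability does not concede poor reliability; no result is given, and the staging rule is not in the document. Step 4's premise that recorded parameters suffice to establish the stage fits rule-based staging at least as well.

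One eCRF holding baseline and outcome data is ordinary, and outcome-aware staging is a possibility rather than a stated procedure. That also stands.

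Finally, which AVAS value enters the model could be left to a statistical analysis plan, which may exist and is not shown. This is fair for the choice of analysed variable. It is weaker for who stages, when, and with what information. Those are data-collection matters, and step 4 itself sets the first of them in a way that leaves the other two open.

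**Conclusion.** The point holds as a permission that the protocol should withdraw. Following step 4 to the letter allows a two-source predictor, and allows the group to stage after the outcomes are on file with no requirement to be unaware of them.

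The document does not show that the analysed predictor is mixed, that staging will be done with knowledge of the outcome, that AVAS varies between raters, or that the same individuals stage and analyse.

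The size of any bias cannot be computed, because the share staged by the group, the share of borderline maps and the inter-rater agreement are all absent. It may be zero. The 5 and 10 point figures show only what the assumed inputs would allow at most, and are not an estimate for this study. The case for amending rests on the exposure of the key predictor and the low cost of closing it.

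**What to change.** Amend step 4 as follows:

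- Derive AVAS for every mapped arm from the recorded vessel parameters by one fixed written rule.
- Apply the rule to an extract without the access type and follow-up fields, and lock the derived stage before merging it with outcomes.
- Use that stage as the predictor in both parts.
- Keep the clinician's score, where one was given, as a separate variable and report its agreement with the derived stage.

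This needs protocol wording and one blinded extract. It needs no new data, since step 4 already has the vessel parameters recorded when the patient is scanned, and it leaves patient care unchanged.

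There is a real trade-off. The primary result will describe rule-derived staging, not staging as assigned in the clinic. The agreement report speaks to the latter only for patients whose clinician chose to score.
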